Institutional Review Board/Ethical Review/Board

(IRB/ERB)

A board or committee (institutional, regional, or national) composed of medical and nonmedical members whose responsibility is to verify that the safety, welfare, and human rights of the patients participating in a clinical trial are protected.

Legal Representative An individual, judicial, or other body authorized under applicable law

to consent on behalf of a prospective patient, to the patient's

participation in the clinical trial.

Patient A study participant who has the disease or condition for which the

investigational product is targeted.

Screen The act of determining if an individual meets minimum requirements

to become part of a pool of potential candidates for participation in a clinical trial. In this study, screening involves invasive or diagnostic procedures and/or tests (for example, radiology and blood draws). For this type of screening, informed consent for these screening procedures

and/or tests shall be obtained.

Subject An individual who is or becomes a participant in clinical research,

either as a recipient of the investigational product(s) or as a control. A

subject may be either a healthy human or a patient.

Treatment-Emergent

Adverse Event

Protocol: ARO-004

(TEAE)

Any untoward medical occurrence that either occurs or worsens at any time after treatment baseline and which does not necessarily have to have a causal relationship with this treatment (also called treatment-

emergent signs and symptoms [TESS]).

ALT alanine aminotransferase
AML acute myeloid leukemia
AST aspartate aminotransferase
CBC complete blood count

CN-AML cytogenetically normal acute myeloid leukemia

Confidential

CT computerized tomography

CR complete response CRF case report form

CRi complete remission with incomplete hematological recovery

CRp complete remission with incomplete platelet recovery

DFS disease-free survival
DLT dose-limiting toxicity
DNA deoxyribonucleic acid
DoR duration of response

ECOG Eastern Cooperative Oncology Group

FDR fixed dose rate

FLT3 FMS-like Tyrosine Kinase 3 GCP good clinical practice

GGTP gamma glutamyl transpeptidase **ICD** informed consent document

ICH International Conference on Harmonization

IHC immunohistochemistryITD internal tandem duplication

LFTs liver function tests

mm millimeter

MRI magnetic resonance imaging

NCI CTCAE National Cancer Institute Common Terminology Criteria for Adverse

Events, Version 4.03

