6.3 Discontinuations

6.3.1 Discontinuations of Patients

The criteria for enrollment must be followed explicitly. If a patient who does not meet enrollment criteria is inadvertently enrolled, that patient should be immediately discontinued from the study drug unless specific approval is obtained from the IRB.

In addition, patients will be discontinued from the study drug but continued to be followed for survival data in the following circumstances:

- The patient experiences unacceptable toxicity as defined in Section 8.7 The patient is non-compliant (see Section 8.10).
- The investigator decides that the patient should be withdrawn, for example due to intercurrent illness that would, in the judgment of the investigator, affect assessments of clinical status to a significant degree. If this decision is made because of a serious adverse event or a clinically significant laboratory value, the study drug is to be discontinued and appropriate measures are to be taken. AROG or its designee is to be alerted immediately (see Section 11.1).
- The patient or attending physician requests that the patient be withdrawn from the study.
- Enrollment in any other clinical trial involving an off-label use of an investigational drug or device or enrollment in any other type of medical research judged not to be scientifically or medically compatible with this study.
- The patient, for any reason, requires treatment with another therapeutic agent that has been demonstrated to be effective for treatment of the study indication. In this case, discontinuation from the study occurs prior to introduction of the new agent.
- The investigator or AROG stops the study or stops the patient's participation in the study for medical, safety, regulatory, or other reasons consistent with applicable laws, regulations, and good clinical practice.

Patients in these circumstances will be followed as per the Study Schedule (appendix IV) and section 11.1.7.

For patients lost to follow-up or undergoing initiation of another drug therapy including allogeneic HSCT, the study schedule will be stopped but patients should be followed for survival data if at all possible.

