Counting Cycle Days: If drug is held or a dose is missed, the missed/held dose should not be made up. Dosing will resume with the next scheduled dose. The patient should enter in the diary the doses as missed. If drug is held or missed for a day or more, the cycle should continue as if uninterrupted. Counting days of a cycle should be ongoing without disruption. The start of cycle 1 is denoted by the ingestion of study drug. The scheduled procedures/visits should comply with the study calendar regardless of amount of study drug administered in a 28 day cycle.

Continuation of crenolanib after allogeneic transplantation as maintenance therapy:

Crenolanib will be held during the transplant period by stopping drug 72 hours prior to start of conditioning and resuming no sooner than 30 days post stem cell infusion.

For patients in CR/CRi after allogeneic transplant, crenolanib may be resumed at the same dose of crenolanib tolerated as induction when crenolanib was held. Patients will complete a daily diary to record the date, time and amount (number of tablets) of crenolanib taken and if it was taken either with or without food (Appendix III). Tablets should be swallowed whole and not be crushed or dissolved/

Patients may receive multiple cycles of treatment as described in Section 8.7.5. Follow up of patients on post-transplant crenolanib is outlined in section 8.2

The investigator or his/her designee is responsible for explaining the correct use of the investigational agent(s) to the patient/site personnel, verifying that instructions are followed properly, maintaining accurate records of study drug dispensing and collection, and returning all unused medication to AROG or its designee at the end of the study. Study medication that has been dispensed but remains unused at the end of the cycle is recorded by the site personnel and either safely discarded, if opened, or returned, if unopened.

Patients will be instructed to contact the investigator as soon as possible if they have a complaint or problem with the study drug so that the situation can be handled. If a patient vomits after drug ingestion, no additional tablets should be taken on that day. Missed doses will not be made up, and leftover drug should be returned to the study site upon patient follow up

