First dose reduction (-1)	180 mg/m ² /day
Second dose reduction (-2)	160 mg/m ² /day

For patients receiving maintenance crenolanib after allogeneic transplant: Start of maintenance crenolanib therapy is intended at the earliest time no sooner than 30 days but no longer than 90 days after allogeneic HSCT. Prerequisites for start of maintenance are a stable dose of immunosuppressive drugs for management or prophylaxis of GVHD or no escalation of therapy for GVHD within 14 days of starting study drug and/or have no more than Grade 2 persistent non hematological toxicity related to the transplant. Patients must have received crenolanib prior to HSCT to continue on to maintenance.

Maintenance therapy will start at the last dose tolerated during reinduction therapy. For example, if the patient was taking 180mg/m2/day prior to proceeding with HSCT, maintenance therapy will resume at 180mg/m2/day.

Dose reductions for non-hematologic toxicities except nausea, vomiting or diarrhea due to crenolanib will be done according to the schema in Table 8.5. For dose level reductions please refer to Table 8.6, and appendix XV. Dose reductions below 140 mg/m2/day are not planned and crenolanib will be stopped.

Table 8.5. Based on NCI CTCAE v4.03, Crenolanib Dose Reduction for Non-Hematologic Toxicities Post Allogeneic Transplant except Nausea, Vomiting, or Diarrhea related to study drug. Use toxicity grade at time of start of next planned cycle. Reassessment may be

performed weekly to determine when to restart drug or dose modify. A 28-day deferment window is allowed to assess toxicities.

Toxicity (NCI Criteria)	Dose modification for patients taking crenolanib post allogeneic transplant
Grade 1 or 2	No dose modification
Clinically significant or persistent grade 2 despite optimal therapy	Hold drug until toxicity resolves to baseline or grade 1 or less. Restart drug at same dose level (Table 8.6).
Grade 3 or 4	Hold drug until toxicity resolves to baseline or grade 1 or less. Restart drug at next lower dose level (Table 8.6).

Table 8.6. Dose adjustments of Crenolanib Post Allogeneic Transplant Maintenance therapy will start at the last dose level tolerated during reinduction therapy and dose adjustments made from that dose.

Current crenolanib dose:	Change crenolanib dose to:
100 mg PO TID*	80 mg PO TID
220 mg/m2/day	200 mg/m2/day
200 mg/m2/day	180 mg/m2/day
180 mg/m2/day	160 mg/m2/day
160 mg/m2/day	140 mg/m2/day

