10.3.1 General Considerations

Statistical analysis of this study will be the responsibility of AROG Pharmaceuticals or its designees. The clinical research physician/scientist and statistician will jointly be responsible for the appropriate conduct of an internal review process for the final study report and any study-related material to be authorized for publication by AROG or its designees.

Safety endpoints will be reported with descriptive statistics for overall study population. For continuous variables, summary statistics will include number of patients, mean, median, standard deviation, minimum, and maximum. Categorical endpoints will be summarized using number of patients, frequency, and percentages.

Any change to the data analysis methods described in the protocol will require an amendment ONLY if it changes a principal feature of the protocol. Any other change to the data analysis methods described in the protocol, and the justification for making the change, will be described in the clinical study report. Additional exploratory analyses of the data will be conducted as deemed appropriate.

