10.3.9 Safety Analyses

All patients will be evaluable for safety. Adverse events that occur after a patient is entered (signs informed consent), but before the patient receives study drug, will not be recorded on the CRF unless the investigator believes that the events may have been caused by a protocol procedure. Safety analyses will include summaries of the incidence of adverse events by maximum CTCAE grade (version 4.03; NCI 2010) that occur during the study treatment period or within 30 days of the last dose of study treatment, regardless of causality or relatedness to study drug. The safety-related outcomes that will be summarized include:

- Adverse events,
- TEAEs,
- SAEs,
- Deaths.
- Discontinuations due to adverse events,
- Extent of exposure to study drug treatment,
- Hospitalizations,
- Use of key concomitant medications (for example, antipruritus medication).

Analyses for data with discrete dates (for example, deaths and concomitant medications) will be performed through 30 days after the patient has been discontinued from study treatment. Adverse events will also be analyzed in this time frame. After 30-day post-discontinuation follow-up, only those SAEs that are thought to be related to study treatment or protocol procedure should be reported immediately to AROG or its designee. For these events, the patient must be followed until the event has resolved or stabilized.

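### The safety tables have no separate transplant period, so early transplant toxicity is counted with crenolanib, and the plan is unclear on which events are collected during the rest of the hold

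*Combined protocol and SAP*

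**What the plan says.** Section 10.3.9 summarises adverse events by maximum CTCAE grade "during the study treatment period or within 30 days of the last dose of study treatment, regardless of causality or relatedness to study drug". It then gives a second anchor: analyses of dated data such as deaths "will be performed through 30 days after the patient has been discontinued from study treatment", with adverse events analysed over the same span. Section 10.3.1 adds: "Safety endpoints will be reported with descriptive statistics for overall study population". Reinduction, transplant and maintenance are not separated, and no table restricted to related events is specified.

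Transplant is a planned path. Bridge to transplant is listed in Section 1.2, and patients may take crenolanib as maintenance afterwards. Section 8.3 describes the interruption as "stopping drug 72 hours prior to start of conditioning and resuming no sooner than 30 days post stem cell infusion", and Section 8.7.1 places the restart "no sooner than 30 days but no longer than 90 days after allogeneic HSCT".

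The documents differ on what the interruption is. Sections 8.3 and 8.7 call it a hold. Section 6.3.1 says that for patients "undergoing initiation of another drug therapy including allogeneic HSCT, the study schedule will be stopped but patients should be followed for survival data". Section 8.12 applies the study schedule only while drug is being taken and restarts it as cycle 1 on resumption. Under Section 11.1.6 and Table 11.1, once 30 days have passed since the last dose or discontinuation, only related serious events are required. Section 11.1.1 says that all adverse events are captured.

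Section 4 defines a treatment-emergent event as "Any untoward medical occurrence that either occurs or worsens at any time after treatment baseline". It names one baseline and does not reset it at the restart.

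**The concern.** Safety and tolerability is the first secondary objective, and there is no comparator. Conditioning and the weeks after infusion bring toxicity of their own while the patient is off crenolanib. A table that is all-cause, keeps the maximum grade and ignores treatment period cannot show which events belong to the drug and which to the transplant. Deaths, serious events and hospitalisations are summarised the same way. The patients affected are those the trial succeeds in bridging to transplant.

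Collection is the second problem. If a site follows Section 6.3.1 and treats transplant as the end of the schedule, non-serious events and unrelated serious events later in the hold may never be recorded. Later analysis can split recorded events by date, but it cannot recover events that were not collected.

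**Working it through.** The plan states no figure on this point to reproduce. The check is day counting.

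**Inputs**
- Drug stops 72 hours, or 3 days, before conditioning (Section 8.3).
- Restart falls between day +30 and day +90 after infusion (Sections 8.3 and 8.7.1).
- The safety window extends 30 days past the last dose (Section 10.3.9).
- A hold totalling 56 days or more leads to discontinuation from study (Section 8.7.4).
- 14 evaluable patients are planned (Synopsis, Section 7.2).
- Conditioning lasts c days from its start to infusion. This is an **assumption**, since the documents give no value; 0 to 14 days is shown.
- The patient takes drug up to the 72-hour stop. This is also an **assumption**; an earlier stop shortens the overlap.

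**Formulas** (day 0 = infusion)
- Last pre-transplant dose: −(c + 3)
- End of 30-day window: −(c + 3) + 30 = 27 − c, which is 30 − 3 = 27 days after conditioning starts, for any c
- Length of hold: 30 + (c + 3) = 33 + c, to 90 + (c + 3) = 93 + c days
- Gap from window end to restart: 30 − (27 − c) = 3 + c, to 90 − (27 − c) = 63 + c days
- Day on which the hold reaches 56 days: 56 − (c + 3) = 53 − c

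| c (days) | Last dose | Window ends | Hold (days) | Gap (days) | 56-day point |
|---|---|---|---|---|---|
| 0 | −3 | +27 | 33–93 | 3–63 | +53 |
| 5 | −8 | +22 | 38–98 | 8–68 | +48 |
| 7 | −10 | +20 | 40–100 | 10–70 | +46 |
| 10 | −13 | +17 | 43–103 | 13–73 | +43 |
| 14 | −17 | +13 | 47–107 | 17–77 | +39 |

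**Reading A: the window is anchored to the last pre-transplant dose.** The first 27 days from the start of conditioning are pooled with crenolanib. The shortest hold, 33 + c days, always exceeds 30, so every patient who resumes has a gap in which only related serious events must be reported.

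**Reading B: the treatment period runs through the hold.** This is the literal result for a patient who resumes, because the last dose then falls in maintenance. All 33 + c to 93 + c drug-free days are pooled. There is no gap by rule, but Sections 6.3.1 and 8.12 leave no scheduled visits at which events would be elicited.

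A patient who never resumes has the Reading A overlap, with no restart to measure a gap against.

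**The 56-day limit.** For each c shown, the 56-day point lies inside the day 30–90 restart window. Section 8.7.4 opens with toxicity delays and does not say whether a transplant hold counts. If it does, it also moves the discontinuation date that anchors the second window in Section 10.3.9.

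**Weight of one patient.** 1/14 = 7.1 percentage points. This is a ceiling for two reasons. Section 7.1 replaces patients treated for less than 28 days for efficacy but assesses everyone for toxicity, so the safety denominator is 14 or more. The shift also requires that the patient had no earlier event of that grade in the row concerned.

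**The case against.** Several counter-arguments have force.

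- **The two halves are alternatives.** A reader might infer that the whole hold is pooled and that part of it also goes uncollected by rule in the same patient. The documents do not support that: full coverage follows from Reading B and the gap by rule from Reading A. What stands under both is pooling of at least the first 27 days from conditioning, given dosing up to the 72-hour stop.
- **Attribution is recorded.** Section 11.1.4 assigns relatedness to each event and Section 11.1.5 has it reported on the CRF. Section 10.3.9 lists what analyses will include without excluding others, and Section 10.3.1 allows exploratory analyses. This mitigates the problem only partly: no planned table uses attribution, and it cannot help with events that were not collected.
- **Large distortions are not shown.** A reader might infer that several transplants would add tens of points, or that a responder would look like a toxicity case. The documents give no number of transplants. Section 8.7.2 expects myelosuppression, so some patients may already have a grade 3–4 haematological event. If the table is by event term, a conditioning event sets only that term's row.
- **Carry-over into maintenance is limited.** No maintenance table is planned, so transplant toxicity cannot at present be miscounted in one. Restart criteria also restrict persistent non-haematological transplant toxicity, though Section 6.2 excludes grade 2 or above while Section 8.7.1 accepts up to grade 2. The baseline matters once a maintenance table is added.
- **Serious events may be covered.** Section 11.1.6 closes by requiring all serious events during trial participation to be reported to the study coordinator, whatever the relationship. That narrows the gap for a site that follows it, but it conflicts with the 30-day rule in the same section.

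**Conclusion.** The point holds in this form: as written, transplant toxicity is mixed into the crenolanib safety tables under either reading of the window, and the documents conflict on which events are collected later in the hold. The overlap is 27 days from the start of conditioning under Reading A, followed by a gap of 3+c to 63+c days before restart. Under Reading B it is the full hold of 33+c to 93+c days, with no gap by rule but no scheduled visits.

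Only transplanted patients are affected. Their number is not given, so the effect on any reported rate cannot be calculated; one patient contributes at most 7.1 points. The net direction is also uncertain, since transplant events are added while later events may be lost. The result rests on drug being taken up to the 72-hour stop and on c, which is assumed. The 27-day overlap does not depend on c.

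**What to change.** **Tables (Section 10.3.9).** Keep the overall all-cause table. Add tables of adverse events, serious events, deaths and hospitalisations for three periods:

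1. *Reinduction*: first dose to the start of conditioning, or to 30 days after the last dose if there is no transplant.
2. *Transplant*: start of conditioning to the first maintenance dose, or to 30 days after the last pre-transplant dose if crenolanib is never resumed.
3. *Maintenance*: first maintenance dose to 30 days after the last dose.

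Show related events within each period, so that delayed drug toxicity appearing after conditioning starts stays visible. In the maintenance table, count treatment-emergent events against the patient's status at maintenance Cycle 1 Day 1.

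**Collection.** State one rule for adverse events during the hold, reconciling Sections 6.3.1 and 8.12 and Table 11.1 with Sections 8.3, 8.7 and 11.1.1. The two serious-event statements in Section 11.1.6 need the same treatment.

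**Related conflicts.** Reconcile the 56-day limit in Section 8.7.4 with the day 30–90 restart window, and the restart toxicity criteria in Sections 6.2 and 8.7.1. Which clinical rule should apply is for the sponsor and investigators.

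**Cost.** Protocol and analysis wording, a few more table columns, and event records kept open through the hold for patients expected to resume. The last item is real work for sites, because no visits are now scheduled in that period.

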10.3.10 Criteria for End of Study

This study will be considered complete following the data cut-off date for the final analysis. Documentation of the data cut-off will be included in the master study file.

After the final analysis, if patients are continuing to benefit from study treatment, they will be allowed to continue receiving study treatment. If patients continue on crenolanib beyond study closure, safety data must be collected. If further data are collected that are not included as part of the final locked database, the postlock data will eventually be combined with the locked database and stored in a data library separate from the locked database.

11. Safety Evaluations and Appropriateness of Measurements

11.1 Safety Evaluations

11.1.1 Adverse Event Definition

An adverse event is defined as any condition which appears or worsens after participation in the study. All adverse events will be captured on the Adverse Event Case Report Form, whether or not it is felt to be related to the trial activities.

11.1.2 Serious Adverse Event Definition

ICH Guideline E6 defines serious adverse events as those events which meets any of the following criteria (Appendix VII):

- Fatal
- Immediately life-threatening
- Results in inpatient hospitalization or prolongation of existing hospitalization
- Results in persistent or significant disability/incapacity
- Results in a congenital anomaly/birth defect

Note: Medical and scientific judgment should be exercised in deciding whether expedited reporting is appropriate in other situations; for example, important medical events may not be immediately life-threatening or result in death or hospitalization, but may jeopardize the patient or may require intervention to prevent one of the outcomes listed in the definition above. Any adverse event is considered a serious adverse event if it is associated with clinical signs or symptoms judged by the investigator to have a significant clinical impact.

Hospitalizations that do not meet these criteria are:

- surgery or procedure planned prior to entry into the trial
- social reason in the absence of an adverse event

Study-specific clinical outcomes of death from PD should be reported as an SAE only if the investigator deems them related to use of the study drug.

